Acceptance and Commitment Therapy (ACT) is a behavioral intervention that targets avoidance and has the capacity to address psychosocial and behavior-related issues that PWH experience. The ACT framework posits that avoidance, particularly avoidance of uncomfortable internal states and situations that trigger such states, influences multiple types of difficulties. ACT helps patients to overcome avoidance by promoting acceptance-based coping and engagement in valued life activities. ACT has one of the strongest bases of empirical support among specific therapies with demonstrated efficacy or effectiveness across an array of conditions, including anxiety, depression, and importantly, dealing with chronic disease. ACT also holds promise for non-diagnostic phenomena such as stigma and ACT is feasible and acceptable among outpatient PWH. Innovative brief ACT interventions appear to be feasible, acceptable, and at least preliminarily, have efficacy. Thus, ACT content and delivery processes have been meaningfully adapted to the specific needs of different populations, but they have not been adapted for out-of-care PWH.

We propose to pilot test an ACT intervention for out-of-care PWH who present with avoidant coping. 'Targeting HIV Retention and Improved Viral load through Engagement' (THRIVE) will aim to help out-of-care PWH overcome the cycle of avoidance coping which can keep PWH out of care and exacerbate/maintain stigma and comorbid mental health difficulties that are common in PWH. Delivering THRIVE in the hospital will increase behavioral therapy initiation and completion, the lack of which is often the greatest obstacle to effective delivery of mental health services for PWH.

Study Flow Diagram

Inclusion and Exclusion Criteria

The target study population is people with HIV who are out-of-care.

Inclusion Criteria

Participants must meet all the following inclusion criteria to participate in this study:

- Hospitalized at Ben Taub Hospital (BTH), Houston, Texas
- At least 18 years of age

- Able to speak English or Spanish
- HIV infection, confirmed by medical record review
- Able to provide informed consent and participate in the study (patients who are temporarily unable to participate will be followed and approached for enrollment if and when they are cognitively and physically capable of consenting and participating)
- HIV VL>1000 c/mL

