- Never in care or currently out of HIV care for HIV, defined as not meeting the 'visit constancy' measure (completed HIV primary care visit in a Houston area clinic in each of the three 4-month intervals preceding admission); or 2 or more "no shows" to HIV primary care visits in a Houston area clinic in the last year. All persons with VL>1000 c/mL would be expected to be seen 3 times in a given year, and "no shows" to clinic visits have been independently predictive of increased morbidity and mortality, especially in Black PWH.
- Endorse one of the two avoidance coping statements with the highest factor loadings on the Avoidant Coping Subscale from the Coping with HIV/AIDS scale.

Exclusion Criteria

All candidates meeting any of the exclusion criteria will be excluded from study participation.

Exclusion criteria are:

- Intending to use a source of HIV primary care other than Thomas Street Health Center (TSHC) after discharge, because their outcomes cannot be evaluated (>70% of PWH hospitalized at BTH intend to use TSHC after discharge)
- In the opinion of the primary medical team caring for the patient, likely to be discharged to an institutional setting, die in the hospital or enter hospice
- Incarcerated or expected to be discharged to prison or jail
- Enrolled in another research study with prospective follow-up
- Pregnant, since pregnant women receive additional efforts to be linked and retained in care
- Admitted with acute psychosis which would preclude informed consent or meaningful participation with the intervention.

Sample Size

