A randomized clinical trial (RCT) pilot of the refined THRIVE intervention (N=35) will be compared to treatment as usual (TAU; N=35). An N=70 is sufficient to establish feasibility and acceptability of a treatment procedure. Feasibility and acceptability are the primary aims of the randomized controlled trial.

The primary goal is to demonstrate the feasibility and acceptability of the THRIVE intervention. Findings from this pilot study will provide useful data that will serve as a basis for enrollment time estimates, attrition estimates, and outcome estimates to support a definitive RCT designed to investigate the efficacy of the THRIVE intervention compared to TAU on retention and VL in hospitalized, out-of-care PWH. The data will also inform sample size and power calculations. We will generate summary statistics of the feasibility and acceptability data. Our pre-defined outcomes (i.e., "benchmarks of success") are: at least 8 participants per month recruited on average (10 per month is the goal); <20% refusal rate among eligible persons; at least 80% receive the outpatient booster phone call; at least 80% of participants alive at 6 months have appointment and 6-month VL data (needed to construct the primary outcome for the definitive full-scale trial); at least 90% of persons who initiate an assessment survey complete it; and at least 80% of the participants in the THRIVE arm rate the intervention positively on the client satisfaction questionnaire.

[Suicide Risk Management](#)

If at any time during the assessments, intervention or booster session a participant indicates suicidal ideation, a research team member will inform the crisis team and/or [name] of the crisis who will assess the participant at the time of the research visit. If the patient does not have a plan or intent, they

will be provided with resources appropriate for the clinical setting (Ben Taub Hospital or Thomas Street Health Center). If they do have a plan or intent, they will be handled by emergency clinical services.

Participant Rights & Confidentiality

Institutional Review Board (IRB) Review

The study protocol and the informed consent document and any subsequent modifications will be reviewed and approved by the IRB at Baylor College of Medicine.

Informed Consent

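### The visit-constancy rule classes every patient diagnosed less than 8 months before admission as out of care, even one who kept every HIV visit

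*Combined protocol and SAP*

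**What the plan says.** The opening of Inclusion and Exclusion Criteria states the target: "The target study population is people with HIV who are out-of-care".

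The Inclusion Criteria put this into operation as "Never in care or currently out of HIV care for HIV, defined as not meeting the 'visit constancy' measure", which requires a "completed HIV primary care visit in a Houston area clinic in each of the three 4-month intervals preceding admission". Two or more missed HIV primary care appointments in the last year is an alternative route to eligibility, joined by 'or'. The reason given for the visit rule is that "All persons with VL>1000 c/mL would be expected to be seen 3 times in a given year".

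Entry also requires "HIV VL>1000 c/mL" and that the patient "Endorse one of the two avoidance coping statements with the highest factor loadings" on the avoidant coping subscale.

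Data Analysis Plan, Analysis Methods, says the pilot will supply "enrollment time estimates, attrition estimates, and outcome estimates to support a definitive RCT" and will inform that trial's sample size and power.

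**The concern.** The rule looks back a full year for everyone, and the reason given for it presumes a year in which visits were possible. For someone diagnosed five months ago, the earliest interval lies wholly before diagnosis. The rule counts that empty interval as a lapse in care.

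The never-in-care wording already covers newly diagnosed patients with no visit. The patients at issue are those who have been linked to care and are attending. They are not never in care and have not dropped out, yet they qualify.

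Two kinds of figure could be affected. These patients count toward the benchmark of at least 8 recruits per month and enter the denominator of the refusal rate among eligible persons. They also enter the composite outcome rates by arm. Both are handed on to the definitive trial.

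**Working it through.** **The rule.** Number the intervals back from admission as 0-4, 4-8 and 8-12 months. Constancy needs a completed visit in all three. A visit in the 8-12 interval requires diagnosis more than 8 months before admission, so anyone diagnosed less than 8 months before fails with certainty.

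**Two constructed records, the same two-monthly attendance, no visit missed.**

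| | Diagnosed | Visits (months before admission) | 0-4 | 4-8 | 8-12 | Class |
|---|---|---|---|---|---|---|
| A | 5 months ago | 0.5, 2.5, 4.5 | yes | yes | none possible | out of care, eligible |
| B | 3 years ago | 0.5, 2.5, 4.5, 6.5, 8.5, 10.5 | yes | yes | yes | in care, not eligible by this limb |

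**Does another criterion catch A?** The missed-appointment limb only adds patients. No exclusion criterion mentions time since diagnosis. The viral load and coping criteria narrow the group but do not measure attendance, and a recently linked patient may keep every visit and not yet be suppressed. So the gap stays open.

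**How often, among recent diagnoses with perfect attendance?** Assume diagnosis uniform over the 12 months before admission, a first visit d months later and regular visits after that. Among those with at least one visit, the share failing is 8/(12 − d):

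- d = 0.25: 8/11.75 = 68%
- d = 0.5: 8/11.5 = 70%
- d = 1: 8/11 = 73%

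This is a share of a narrow subgroup, not of enrolees. The documents do not give the share of enrolees.

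**The plan's own precision figure.** Sample Size states 15 to 17 points for a group rate between 30% and 65% with 35 per group. The half-width 1.96 × √(p(1 − p)/35) gives 15.2 points at 30%, 16.6 at 50% and 15.8 at 65%, so the figure reproduces. The issue here does not alter it.

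**Precision of the arm difference.** At 30% versus 50%: 1.96 × √((0.30 × 0.70 + 0.50 × 0.50)/35) = 22.5 points.

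**Illustrative dilution.** All rates here are assumptions: 30% versus 50% in target patients, 65% in both arms for affected patients, and affected share f. The observed difference is (1 − f) × 20 points. With p̄ the mean of the two rates, n per arm (two-sided 5%, 80% power) is [1.96√(2p̄(1 − p̄)) + 0.842√(p₁(1 − p₁) + p₂(1 − p₂))]² / (p₂ − p₁)².

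| f | TAU | THRIVE | Difference (points) | n per arm |
|---|---|---|---|---|
| 0 | 30.0% | 50.0% | 20 | 93 |
| 5% | 31.8% | 50.8% | 19 | 105 |
| 10% | 33.5% | 51.5% | 18 | 118 |
| 20% | 37.0% | 53.0% | 16 | 151 |

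Taking 80% instead of 65% for the affected patients changes n by at most 1 per arm (93, 105, 119, 152).

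**The case against.** The strongest reply concedes the logic and disputes the consequence. An affected patient must be hospitalised, have a viral load above 1000 c/mL, endorse avoidance coping, intend to use the study clinic and have kept every visit. That may be a small group. The Scientific Rationale itself says avoidance coping predicts poor clinical outcomes and poor re-engagement after hospitalization, so high success in both arms cannot be taken for granted. If these patients benefit as others do, there is no dilution. Randomisation protects the comparison, no hypothesis test is planned, and feasibility and acceptability are the primary aims. A fixed 12-month look-back is also simple to apply. All of this stands as a limit on size. None of it makes the classification correct for a patient such as A.

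Three stronger readings are tempting, and the documents do not support them.

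- **The pilot's effect estimate is diluted and the definitive trial will be mis-sized.** The share, the success rate and the absence of effect in these patients are all assumed. If the definitive trial keeps the criterion, the estimates suit the population it will enrol, though not the stated target. If it tightens the criterion, sizing on a diluted difference would make it too large, not underpowered.
- **The baseline retention-in-care variable is wrong.** Summary of Measures at Each Evaluation lists it but gives no derivation.
- **The Houston-area wording needs the same repair for people who recently moved.** Read literally, it does fail them. But the record sources described are the Harris Health EMR and a regional six-county database, and requests for outside records are described for participants, not for screening. A clause counting visits elsewhere could not be applied at screening from the sources described.

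**Conclusion.** The misclassification is certain from the text: failure below 8 months since diagnosis follows from the interval boundaries and needs no assumption. It conflicts with the stated target population and with the one-year rationale for the rule.

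The consequence is minor. With assumed shares of 5% to 20%, success the same in both arms for affected patients, and a 20-point effect in the rest, the difference moves by 1 to 4 points against a half-width of about 22. The effect on recruitment figures cannot be sized from the documents. The reason to correct the rule is that the criterion and the pilot's estimates may both be carried into the definitive trial.

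**What to change.** Amend the visit limb of the Inclusion Criteria along these lines:

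> Visit constancy is assessed only over complete 4-month intervals before admission that fall wholly after HIV diagnosis. Where there is no such interval, a patient with at least one completed HIV primary care visit is not out of care under this limb.

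Leave the never-in-care and missed-appointment limbs unchanged.

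Complete intervals are preferable to counting the part-interval just after diagnosis. Someone diagnosed 4.5 months ago and first seen one month later would have an empty half-month fragment and still fail. Under the uniform-diagnosis assumption used in the working, a part-interval rule misclassifies 2d/(12 − d) of perfect attenders with at least one visit: 4%, 9% and 18% for d = 0.25, 0.5 and 1 month.

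Take time of diagnosis from the chart review or in-person screening already described under Screening.

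If enrolment has started, or if the sponsor means to include recently linked patients, say so. Flag them at baseline from the questionnaire item on when the participant first learned of the diagnosis and from the abstracted visit data, and report the recruitment rate and the composite rates with and without them.

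The cost is one extra screening check and a slightly smaller eligible pool. A patient diagnosed less than 4 months ago who attended once and then stopped would qualify only through the missed-appointment limb.

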Since hypothesis testing is not recommended for pilot studies, no formal hypothesis testing on the efficacy of the intervention will be performed in this pilot trial for the primary and secondary outcomes. However, estimates of the difference or the relative ratio between arms, with 95% confidence intervals, will be obtained that will provide information on the direction and possible range of the intervention effect which may be used as a basis to support a larger RCT. We will compare the ACT group to the TAU group on retention in care and undetectable VL 6 months after hospital discharge with descriptive statistics calculated for these primary outcomes. Assuming a composite outcome (retention in care and VL improvement) of between 30% and 65%, a sample size of N=35/group will allow us to estimate the outcome rate for each group to within 15 to 17 percentage points (95% CI). Estimates of the difference between treatment arms will also be assessed for exploratory outcomes, including mental health, stigma, and coping. Likewise, descriptive statistics will be computed for the demographic, clinical, and baseline variables to describe the characteristics of the pilot study sample population. These analyses

will also help validate our methods and data gathering techniques. These descriptive analyses will also be performed for the sub-populations that we anticipate will have more difficulty relinking to outpatient HIV care (e.g., substance abuse).

Study Timeline

Timeline	Yr 1				Yr 2		
Recruit 70 pts (10/m): follow for 6m	X	X	X	X	X		
Review EMR, analyze data, finalize protocols, publish					X	X	

We anticipate enrolling 8-10 persons per month and should complete enrollment in < 9 months. We will need 6 months to follow the last participants. We will also need time for data analysis and final protocol revisions. The pilot study will be completed within 18 months.

Recruitment, Consent, and Enrollment

Screening

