The Harris Health EMR, an Epic product, is accessible via Citrix on any computer. Researchers can review the entire EMR from their research offices, including discharge summaries, inpatient and outpatient notes, laboratory results, all appointment schedules, and prescriptions. Epic data include appointment, laboratory, and ART data on all patients seen at BTH, TSHC or one of its satellite HIV clinics from 2002 to present. Appointment data include all visits at TSHC, including HIV primary care, mental health, and chemical dependency counselor visits. Clinic visit data include whether the visit was kept, missed, cancelled, or rescheduled. Dates of hospitalization at BTH are included. Completed and missed visit data will be abstracted from Epic. The Centralized Patient Care Data Management System (CPCDMS) is a regional database in which clients must be registered to receive medical and case management services funded by the 6-county Ryan White Part A funds. CPCDMS will indicate if participants have transferred care from TSHC to other Ryan White-funded providers, substantially reducing the chance of misclassifying patients regarding care re-engagement.

[6-month Viral Load](#)

All patients have a VL done as standard of care in the hospital. We will obtain 6-month VL by study phlebotomy in the field (not at the clinic, to avoid biasing participants) if none are available in the EMR, and review the EMR for additional VLs to minimize missing data. All VL assays will be conducted by the BTH laboratory, a fully certified clinical laboratory that performs all HIV-related laboratory studies for TSHC and BTH.

Data Collection and Quality Assurance

REDCap

All data collection forms will be available through a REDCap (Research Electronic Data Capture) database and patients can directly enter data into these forms. They will enter data into a central database through a study computer. This will eliminate error in data entry, and reduce time necessary for data entry, cleaning and analysis. Range checks will be programmed into the data entry system when the nature of the data allows so that it will not permit invalid values to be entered into the database.

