When a data collection session is completed, the research coordination will review electronic forms for completeness and validity. The research coordinator will resolve all queries and will enter an override for all values that have been confirmed as being accurate. Reports will also be run periodically to confirm or correct questionable values. All changes will be tracked through the REDCap audit trail. Assessments completed on paper will be entered into REDCap by the research coordinator.

The data entered into the REDCap database is stored on servers at Baylor College of Medicine and is backed-up on a regular basis.

Strategies for minimizing missing data

1. Reviewing all surveys for completeness before finalizing.
2. Reviewing all electronic medical records for internal and external records.
3. Requesting medical records for participants who report use of external facilities.

Protocol Deviations

Protocol deviations will be recorded as they are known to happen on a hard-copy form and then entered in the study's Tracking Database to compile an electronic log for reporting purposes. Quarterly hard-copy-to-electronic-copy audits of Protocol Deviation forms and audits of consent forms will be performed.

Monitoring

Data will be routinely monitored at the time of data collection. REDCap will be used to collect data and the researchers will be prompted at the end of each session to check missing entries. Regular team meetings will be held where researchers can report ongoing data collection concerns to ensure proper adherence to the protocols and high-quality data collection. Audio files will be stored on a secure BCM server. Only the participants' ID will be used to identify the participants. Coordinators will ensure the data is de-identified.

Summary of Measures at Each Evaluation

Type of Measure	Measures	Baseline Visit	THRIVE: In-hospital sessions (4hrs.)	THRIVE: Phone booster session (.5 hrs.)	Post-discharge	2 wk.	3 mo.	6 mo.
Characterize Sample. Possible Covariates	Demographic/ Medical Information	X						
	Coping Skills	X			X	X		
Primary Outcomes	Retention in HIV Care	X					X	
	HIV VL	X					X	
Exploratory: Stigma & Mental Health	Stigma	X			X	X		
	Depression, Anxiety, and Stress	X			X	X		
	Substance Use	X			X	X		
Treatment Satisfaction	Client Satisfaction		X					

Data Collection Instruments

Demographics/Medical Information

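### Do the 6-month outcome rates need a written rule for deaths and missing viral loads before the 15 to 17 point precision can stand?

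*Combined protocol and SAP*

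**What the plan says.** The Sample Size section rules out formal efficacy testing. It assumes a composite rate of 30% to 65% and states that "a sample size of N=35/group" "will allow us to estimate the outcome rate for each group to within 15 to 17 percentage points (95% CI"). It adds that "estimates of the difference or the relative ratio between arms, with 95% confidence intervals, will be obtained", to show the direction and possible range of the effect for a larger trial.

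The Analysis Methods section makes feasibility and acceptability the primary aims. One benchmark is that "at least 80% of participants alive at 6 months have appointment and 6-month VL data (needed to construct the primary outcome"; the sentence goes on to say that this outcome belongs to the later full-scale trial. The same section expects the pilot to yield "attrition estimates, and outcome estimates to support a definitive RCT".

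On data capture, the 6-month Chart Review section says "Completed and missed visit data will be abstracted from Epic". The 6-month Viral Load section provides a viral load "by study phlebotomy in the field (not at the clinic, to avoid biasing participants) if none are available in the EMR"; the Blood Draw section says the same, while the Evaluation Overview states the field draw without that condition. The list headed "Strategies for minimizing missing data" has three items, all about prevention. No section names an analysis population or a counting rule for deaths or missing viral loads.

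**The concern.** A precision based on 35 per group holds only if nearly all 35 are in the denominator, so people who died or have no viral load must be counted somehow. The plan does not say how. The data benchmark tolerates up to 20% missing among those alive, and it can be read as describing a rate among participants with data. Two analysts could therefore choose different denominators.

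The loss is also unlikely to be random. Someone who returns to clinic will usually have a viral load in the record, whereas someone who stays away depends on the field draw. If the composite requires both components (an assumption, since the plan does not define it), a person charted as not retained is a known failure, yet a complete-case set would drop that person. Rates would then be too high. If the arms differed in how many were dropped, the difference carried into planning the larger trial would be distorted as well.

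**Working it through.** **1. The plan's figure.** Inputs from the Sample Size section: n = 35 per group, p from 0.30 to 0.65, 95% confidence. Half-width = 1.96 × √(p(1 − p)/n).

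| n per group | p = 0.30 | p = 0.50 | p = 0.65 |
|---|---|---|---|
| 35 | 15.2 | 16.6 | 15.8 |
| 34 | 15.4 | 16.8 | 16.0 |
| 28 | 17.0 | 18.5 | 17.7 |

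The first row reproduces 15 to 17 points. With 34 it still rounds to that range. The last row applies the 80% floor to a full arm (0.8 × 35 = 28) and costs about 2 points.

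**2. Effect on one arm's rate.** If p is the rate among those with data and m of 35 are missing, counting the missing as failures lowers the rate by p × m/35.
- p = 0.50, m = 7: 0.50 × 7/35 = 10.0 points.
- p = 0.50, m = 2: 0.50 × 2/35 = 2.9 points.
- Over the plan's range with m = 7: 0.30 × 7/35 = 6.0 to 0.65 × 7/35 = 13.0 points.

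**3. Effect on the difference.** Assumed counts, not in the documents: 16 successes in THRIVE and 12 in TAU, hence 19 and 23 failures; no deaths; all missing participants are failures. Intervals are Newcombe 95%.

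| Missing THRIVE/TAU | THRIVE | TAU | Difference (points) |
|---|---|---|---|
| None dropped | 16/35 = 45.7% | 12/35 = 34.3% | +11.4 (−11.1 to 32.4) |
| 3/4 (90% with data) | 16/32 = 50.0% | 12/31 = 38.7% | +11.3 |
| 6/8 (80% with data) | 16/29 = 55.2% | 12/27 = 44.4% | +10.7 |
| 7/7 (80%) | 16/28 = 57.1% | 12/28 = 42.9% | +14.3 |
| 3/11 (80%) | 16/32 = 50.0% | 12/24 = 50.0% | 0.0 (−24.8 to 24.8) |

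The 3/4 and 6/8 rows are what the suspected mechanism produces when failures go missing at the same rate in both arms. For 14 missing among 42 failures that rate is one third, so 19/3 ≈ 6 and 23/3 ≈ 8. Both arm rates rise and the difference hardly moves.

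The last row needs 3/19 = 16% of THRIVE failures missing against 11/23 = 48% of TAU failures, with data availability exactly at the 80% floor. Nothing in the documents gives a reason to expect that.

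**The case for a change.** The strongest case for a change is this. The arm rates and their difference are what the pilot passes to the larger trial, and the study is unblinded. Participants were recruited because they were out of care with a viral load above 1000, so loss and death are foreseeable. THRIVE aims to change retention, so loss could differ by arm. With more extreme splits of 14 missing, the complete-case difference in the example runs from −3.7 (2/12) to +21.5 (9/5). A one-paragraph rule would cost little.

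Part of this stands. The plan is silent, and the choice of denominator can move an arm's rate by about 10 points at the tolerated level of loss. Unequal loss would move the difference too.

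The rest is weaker. The 80% benchmark concerns data capture and looks to the definitive trial's outcome; it sets no denominator for the pilot's rates and does not conflict with the Sample Size section. Several measures aim at the people most likely to be missed: the field draw where the record has no viral load, contact calls at 2, 8 and 18 weeks, requests for outside records, transfer tracking through the regional database, and separate payment for the blood draw.

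A missing-as-failure rule would be one defensible choice among several. It would also need a 6-month retention criterion, which the plan does not give. Nor would a complete-case result beside it show how far it understates the rate, because complete cases say nothing about how the missing people fared.

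**Conclusion.** No change to the plan follows. The 15 to 17 points is correct for the 35 per group it is stated for, and no rule in the plan gives a wrong result. What is missing is a written convention for a secondary, descriptive summary.

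The pilot makes no efficacy claim that the convention could overturn. At 7 missing of 35, the largest shift in an arm's rate over the plan's assumed range is 13.0 points, inside the 15 to 17 points already conceded for that rate. In the example, even the 0.0 and +11.4 results have intervals that overlap heavily and both include zero. Reporting the data benchmark requires counting who was alive and who had data, and attrition is itself something the pilot will estimate, so readers will see the overall scale of the loss. The plan does not promise that count by arm. A competent analyst would give it, state the denominator and show the result under the alternative.

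This rests on three assumptions: loss stays near or better than the 80% benchmark, it is not strongly different between arms, and the illustrative counts are typical of the plan's 30% to 65% range. If loss proved heavy and one-sided, the difference should not be used for planning without bounds that count the missing first as failures and then as successes.
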